3.3 Assessment Visit (One Month after the Treatment Visit)

- Participants will answer the questionnaire about the medications, alcohol and marijuana as well as the other therapies they use for pain relief.
- They will be given the BPI NRS pain severity scales and the ODI questionnaire.
- They will once again be assessed, marked, measured and treated: this time participants in all treatment groups will be instructed on how to do the SIFFT and the corresponding corrective exercises. All of them will also receive the pelvic support belt.
- Those in group 1 will report on their use and effectiveness of the corrective exercises. They will then be fitted with a pelvic support belt.
- Those in group 2 will report on their use and the effectiveness of the pelvic support belt. They will then be taught the SIFFT and how to use the exercise corresponding to the direction of their sacroiliac malrotation.
- Those in group 3 will be instructed on how to do the SIFFT and the corresponding corrective exercises. They will also receive the pelvic support belt.
-

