4.2 Data Collected on All Participants with Nonaligned PSISs

4.2.1 At all visits

- Date of questionnaire (randomization and first treatment visit, one month assessment visit and two month reassessment visit)
 - Use of medications, cannabis, alcohol.
 - Use of other treatments: acupuncture, yoga, core exercises, chiropractic manipulation, massage, physiotherapy and other treatments.
 - The (ODI) questionnaire (appendix 2)
 - the BPI NRS Pain Severity Scale (appendix 1): On a scale of 0 (no pain) to 10 (worst imaginable pain) pain in the last 24 hours compared to previous recorded pain level (the participant will have this information available)
 - on average
 - at its worst
 - at its best
 - right now

the average of these values as well as the pain "right now" will be recorded.

4.2.2 At the Treatment visit and the One Month Follow-Up Visit:

- On which side the painful sacroiliac sprain is located and whether it is anteriorly or posteriorly rotated.
- Distance in centimetres between the lowest and the highest PSIS: before and, for group 1 participants, after the corrective exercise.
- Pain score 0 (no pain) to 10 (worst imaginable pain) following the exercise, for group 1 participants.
- Impression of pelvic support belt for group 2 participants

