4.2.3 At the One Month Assessment Visit

- For group 1 participants Frequency of exercise use (0 = not at all, or number of times per week)
- Effectiveness of the corrective exercise in correcting pain (0 = not at all, 1 = sometimes, 2 = most of the time, 3 = always)
- Side effects of the corrective exercise

For group 2 participants

- Satisfaction with use of the pelvic support belt (0 = not at all, 1 = mildly satisfied, 2 = moderately satisfied, 3 = very satisfied)
- Was the pelvic support belt worn during the day? (0 = not at all, 1 = sometimes, 2 = most of the time, 3 = always)
- Was the pelvic support belt worn at night? (0 = not at all, 1 = sometimes, 2 = most of the time, 3 = always)
- Side effects of the pelvic support belt

For all participants

- Perceived need for further treatment 0 = not at all, 1 = possibly, 2 = probably, 3 = certainly)

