5.1.3 Other Measurements

- Change in pain level, immediately before and after the corrective exercises at
 - the treatment visit for members of group 1
 - the one-month follow-up assessment visit.
 - the two month reassessment visit
- Change in average pain level between the
 - treatment visit
 - and the one-month follow-up visit.
- Number of times the exercise was used per week
- Perceived effectiveness of the exercise
 - when first used with the physician
 - one month later,
 - and two months later for group 1
- How often the pelvic support belt was used during the day at the one month follow-up assessment visit for group 2.
- How often the pelvic support belt was used during the day at the 2 month reassessment visit for all participants.
- How often the pelvic support belt was used during the night at the follow-up assessment visit for group 2.
- How often the pelvic support belt was used during the night at 2 month reassessment visit for all participants.
- Perceived effectiveness of the pelvic support belt when first used and after one month of use for all participants.
- perceived effectiveness of the pelvic support belt when first used and after two months of use for group 2.

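### Section 5.1.3 plans before-and-after exercise pain and belt effectiveness outcomes that the section 4.2 collection lists only partly supply

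*Combined protocol and SAP*

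**What the plan says.** **Exercise.** Section 5.1.3 lists this outcome: "Change in pain level, immediately before and after the corrective exercises at" three visits. The first bullet is limited to one arm ("the treatment visit for members of group 1"). The one-month bullet and the last one ("the two month reassessment visit") carry no limit.

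Section 4.2.2, which covers the treatment and one-month visits, collects "Pain score 0 (no pain) to 10 (worst imaginable pain) following the exercise, for group 1 participants". It restricts the post-exercise distance between the PSISs in the same way: "for group 1 participants, after the corrective exercise". Yet section 3.3 says of the one-month visit that "this time participants in all treatment groups will be instructed on how to do the SIFFT and the corresponding corrective exercises". Section 4.2.4 (month 2) lists frequency, effectiveness and side effects of the exercise, but no pain score taken after it. The score before the exercise is available throughout, because section 4.2.1 records current pain from the BPI at all visits.

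**Belt.** Section 5.1.3 plans "Perceived effectiveness of the pelvic support belt when first used and after one month of use for all participants", and a further comparison at two months for group 2. Section 4.2 contains an unscaled impression of the belt (group 2, section 4.2.2), "Satisfaction with use of the pelvic support belt" on a 0-3 scale (group 2 at month 1, no group limit at month 2), and how much the belt was worn. The exercise has its own 0-3 effectiveness item; the belt has none. Section 3.3 does say that group 2 will report on the belt's effectiveness at one month.

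**The concern.** An outcome can be reported only if the forms collect it, and pain just after an exercise cannot be reconstructed later. Groups 2 and 3 are first taught the exercise at the one-month visit. That visit therefore offers 40 first-use responses on top of the 20 from group 1 at the treatment visit. Under section 4.2.2 none of the 40 is kept, and the month-1 figure would come only from people who were taught the exercise a month earlier.

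The introduction (section 1.1) treats relief from the exercise as a sign that the pain is sacroiliac rather than lumbar. Immediate response is the most direct information the trial gathers on that idea, so losing two thirds of the possible first-use responses is a real, if secondary, loss. For the belt, the risk is that whoever writes the report must decide afterwards whether impression or satisfaction stands for effectiveness.

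**Working it through.** The plan gives no figure of its own for this point. The check sets each section 5.1.3 outcome against the section 4.2 lists and counts participants. The only input is section 2.2: 20 per group, 60 in all. Dropout is ignored.

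**Post-exercise pain score**

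| Visit | Planned in 5.1.3 | Collected under 4.2 |
|---|---|---|
| Treatment | 20 (group 1) | 20 |
| Month 1 | 60 (no limit) | 20 (group 1) |
| Month 2 | 60 (no limit) | 0 |
| Total | 20 + 60 + 60 = 140 | 20 + 20 + 0 = 40 |

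Coverage is 40/140 = 29% of planned participant-visits. If section 5.1.3 is instead read as group 1 throughout, the plan is 20 + 20 + 20 = 60, of which 40 are collected (67%), and month 2 is still empty.

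First-use responses: group 1 at the treatment visit gives 20, and groups 2 and 3 at month 1 could give 20 + 20 = 40. Section 4.2 keeps 20 of 60.

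**Precision at month 1, for illustration.** The documents give no SD for this change, so an SD of 2 points (range 1.5 to 2.5) is assumed. The 95% half-width is t(0.975, n−1) × SD / √n.

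- n = 20: 2.09 × 2 / 4.47 = 0.94 (0.70 to 1.17).
- n = 60: 2.00 × 2 / 7.75 = 0.52 (0.39 to 0.65).

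**Belt effectiveness.** Groups 1 and 3 receive the belt at month 1, so their first use falls at that visit and one month of use falls at month 2.

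| Time point | Planned | Item named effectiveness in 4.2 | If impression and satisfaction count as proxies |
|---|---|---|---|
| First use | 60 | 0 | 20 (group 2 impression) |
| After one month of use | 60 | 0 | 20 (group 2, month 1) + 40 (groups 1 and 3, month 2) = 60 |
| After two months of use, group 2 | 20 | 0 | 20 |
| Total | 140 | 0 | 20 + 60 + 20 = 100 |

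The procedures in section 3.3 add an effectiveness report from the 20 group 2 participants at month 1, for which section 4.2.3 provides no item.

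**The case against.** The strongest reply is that these are other measurements, which section 5.2 reports only as averages and standard deviations. No hypothesis, test or confidence interval depends on them, and ODI and BPI are collected at every visit. That stands in full and sets the weight of the point. It also means that the half-widths above are only illustrative.

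Some stronger readings are tempting, and the documents do not support them:

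- A reader might infer that belt effectiveness is never asked. Section 3.3 has group 2 report it at one month, and section 4.2 collects impression and satisfaction, which could serve as proxies if the plan said so. What remains is a mismatch of terms, the missing item behind the section 3.3 report, and a true gap at first use for groups 1 and 3.
- A reader might infer that month 2 has no before-or-after pain at all. Only the score after the exercise is absent.
- A reader might infer that the trial loses its only evidence on the diagnostic idea. Group 1's treatment-visit response is fully planned and collected, the 0-3 exercise effectiveness item also bears on it, and diagnosis is not among the hypotheses in section 1.2.
- A reader might infer that a planned PSIS outcome is lost. Section 5.1.3 lists none, and the exercise procedure in section 3.2.2 already re-marks the PSISs afterwards. The group 1 limit on recording that distance is worth lifting, but no listed outcome depends on it.

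Two further replies stand in part. Taking the month-1 bullet as all groups is an inference, though a fair one, since only the first bullet is limited. The available text also does not establish that the exercise is performed at the two-month visit: the contents list a section 3.4 for that visit, but the body as available runs from 3.3 to 3.5.

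**Conclusion.** The mismatch is real and minor. Under section 4.2 as written, the planned change in pain across the exercise rests on 20 of 60 participants at month 1, all from group 1, and on none at month 2. The 40 first-use responses in groups 2 and 3 are not recorded. Belt effectiveness has no named item in section 4.2, nothing is collected on the belt at first use for groups 1 and 3, and the group 2 report announced in section 3.3 has no item.

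The counts assume full recruitment, no dropout, and the unrestricted bullets in section 5.1.3 read as all groups. On the narrowest reading (group 1 only) the month-1 gap closes, but month 2 stays empty and the belt mismatch is unchanged. The primary and secondary outcomes are unaffected.

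**What to change.** Reconcile sections 5.1.3, 4.2 and 3.3:

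1. In section 4.2.2, replace the limit to group 1 on the post-exercise pain score with every participant who performs the exercise at that visit. Do the same for the post-exercise PSIS distance, so that what is already marked is also recorded.
2. State whether the exercise is performed at the two-month visit. If it is, add a post-exercise pain score to section 4.2.4. If not, delete that bullet from section 5.1.3. No extra score before the exercise is needed.
3. For the belt, choose one of two routes. Either add a 0-3 effectiveness item worded like the exercise item, at first use and after one month of use for all participants, and at month 2 for group 2. In visit terms this means the treatment visit for group 2, and months 1 and 2 for everyone. Or reword the section 5.1.3 bullets in terms of the impression and satisfaction items and the groups in which they are collected, and provide an item for the group 2 report in section 3.3 or align that sentence.
4. When reporting month 1, show group 1 (repeat users) separately from groups 2 and 3 (first use).

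The cost is one extra pain rating and one recorded level for about 40 participants at a visit they already attend, plus at most one form item. Section 3.2.2 already has the examiner re-mark the PSISs and ask about remaining pain after the exercise, so step 1 mainly records what is already done.

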4.2.3 At the One Month Assessment Visit

- For group 1 participants Frequency of exercise use (0 = not at all, or number of times per week)
- Effectiveness of the corrective exercise in correcting pain (0 = not at all, 1 = sometimes, 2 = most of the time, 3 = always)
- Side effects of the corrective exercise

For group 2 participants

- Satisfaction with use of the pelvic support belt (0 = not at all, 1 = mildly satisfied, 2 = moderately satisfied, 3 = very satisfied)
- Was the pelvic support belt worn during the day? (0 = not at all, 1 = sometimes, 2 = most of the time, 3 = always)
- Was the pelvic support belt worn at night? (0 = not at all, 1 = sometimes, 2 = most of the time, 3 = always)
- Side effects of the pelvic support belt

For all participants

- Perceived need for further treatment 0 = not at all, 1 = possibly, 2 = probably, 3 = certainly)

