In 2018 I did a chart review of 180 cases of low back pain in which I tested those who did not have lumbar pain using the SIFFT^x. I treated them with the appropriate exercise depending on the direction of the sacroiliac rotation. From this review, I found 16 cases of pain coming from the lumbar spine (9%). Of the remaining 164 given the appropriate 2 minute exercises, 78% found pain relief of which two thirds left the office entirely pain free. At that time, I also prescribed a pelvic support belt as, generally, a malrotated pelvis is an unstable pelvis^{xi}. As soon as the pelvis becomes malrotated again, the pain recurs. As the corrective exercise and pelvic support belt are two different treatments, the current research project will study them first separately for one month, then on follow-up after they have been used together for one month.

The aim of this study is to determine whether the pain relief and improved back function is temporary or if it can be reproduced and sustained by the patient at home, as needed with these two treatments. In order to test the effectiveness of each treatment alone and when they are combined, two sub-studies will be carried out as follows:

The first study is a superiority trial with a delayed control.

Population: ambulatory people between the ages of 19 and 90 suffering from low back pain, not of lumbar spine or hip origin, for at least three months.

Intervention 1 : teaching participants how to detect pelvic malrotation using the SIFFT then prescribing a two-minute exercise to correct pelvic malrotation, depending on its direction.

Intervention 2: prescribing a pelvic support belt to stabilize the pelvis.

Control: waiting list for one month, using usual treatments such as medications, alcohol and other drugs, chiropractic and other manipulation and physical therapy.

Outcome: a clinically significant change in Brief Pain Inventory (BPI) NRS pain score or in Oswestry disability Index (ODI) for low back pain.

Time: outcomes measured at baseline and after one month of using the assigned treatment at home.

The second study is a one month follow-up of the combined treatments.

Population: all previous study participants

Intervention: teaching all participants how to detect pelvic malrotation using the SIFFT then a two-minute exercise to correct pelvic malrotation depending on its direction followed by prescription of a pelvic support belt.

Control: BPI NRS pain severity score and ODI at one month assessment

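### Month 1 has no side-effect question common to all three groups, so symptoms outside the pain and disability scales lack a comparator in the only randomised treated-versus-waiting period

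*Combined protocol and SAP*

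**What the plan says.** Section 4.2.3 sets the month-1 items by group. Group 1 is asked about exercise frequency, its effectiveness and "Side effects of the corrective exercise". Group 2 is asked about belt satisfaction, wear and "Side effects of the pelvic support belt". The only item there for everyone is "Perceived need for further treatment 0 = not at all, 1 = possibly, 2 = probably, 3 = certainly", which is not a harm question.

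Section 3.3, which describes the same visit, adds no harm question. It also gives both treatments to every group from that visit onward. Until then group 3 is on a "waiting list for one month, using usual treatments such as medications, alcohol and other drugs, chiropractic and other manipulation and physical therapy" (section 1.1).

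Section 4.2.1 collects the ODI, the BPI pain items, other treatments and "Use of medications, cannabis, alcohol" at all visits in all groups. Section 5.1 compares change in ODI and BPI between each treated group and the waiting list at month 1. Side effects are not listed in section 5.1.3, so under section 5.2 they fall into the remaining data, to be summarised by average and standard deviation.

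**The concern.** Both side-effect items ask the participant to attribute a symptom before reporting it. That is hard to do here. Section 1.1 says the condition itself produces groin, hip-region and knee pain, and section 3.2.2 describes a forceful exercise held for two minutes. A group 1 participant with new groin pain has to decide whether the exercise or the disease caused it. If they decide on the disease, the item does not capture the symptom. If they report it, there is no rate from the waiting list to set beside it.

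The two treated groups answer different questions, so they cannot be compared with each other on side effects either. After month 1 no group remains off both treatments, so the background rate cannot be obtained later within the trial.

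**Working it through.** **1. Which groups answer what at month 1** (sections 3.3, 4.2.1 and 4.2.3)

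| Item | Group 1 | Group 2 | Group 3 |
|---|---|---|---|
| Exercise side effects | yes | no | no |
| Belt side effects | no | yes | no |
| Neutral new-symptom question | no | no | no |
| ODI, BPI | yes | yes | yes |
| Medication, cannabis, alcohol, other treatments | yes | yes | yes |
| Perceived need for further treatment | yes | yes | yes |

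No side-effect item is shared by any two groups. In the supplied layout the group 1 label runs into the first bullet of section 4.2.3, so its reach over the next two bullets is inferred. The group 2 and all-participants labels that follow support this reading, and an exercise-effect item could not apply to group 3 before it has been taught the exercise.

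**2. What the ODI and BPI can and cannot pick up**

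- They can show worsening of pain or function in all groups. The BPI items in Appendix 1 are not restricted to the back, so new pain elsewhere can raise the score.
- They do not record the site of pain, so new pain elsewhere is not identifiable as such.
- In Appendix 1 the worst and least BPI items cover 24 hours and another asks about the present. The ODI pain item in Appendix 2 also refers to the present. A flare in week 1 that has settled can be missed.
- Neither scale covers skin irritation, which section 3.2.3 anticipates with the belt.
- Under sections 3.5 and 3.5.1 the last data are entered for those lost to follow-up or refusing further questionnaires. A participant who leaves before month 1 because of harm would then carry the baseline value and count as unchanged.

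**3. Month 2 does not help.** Section 4.2.4 lists both side-effect items without group restriction, but by then all groups have both treatments.

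**4. What a common item would yield with 20 per group**

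Input: 3 × 20 = 60, which agrees with section 2.2. That section gives no power, effect size or event rate, so the sample size itself cannot be re-derived. The documents give no side-effect rates; all rates below are assumptions.

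Exact (Clopper-Pearson) two-sided 95% intervals, n = 20:

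- 0/20: upper limit = 1 − 0.025^(1/20) = 16.8%
- 1/20: 0.1% to 24.9%
- 5/20: 8.7% to 49.1%

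Fisher's exact test against 0/20 in the waiting list, two-sided:

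- 4/20: 2 × C(20,4)/C(40,4) = 2 × 4,845/91,390 = 0.106
- 5/20: 2 × C(20,5)/C(40,5) = 2 × 15,504/658,008 = 0.047

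Power at 20 per group, two-sided 0.05. The last column is n = [1.96√(2p̄(1−p̄)) + 0.8416√(p₁(1−p₁)+p₂(1−p₂))]²/(p₁−p₂)², where p̄ is the mean of the two rates:

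| Assumed rates | Power, normal | Power, Fisher | n per group for 80% (normal) |
|---|---|---|---|
| 5% v 20% | 0.30 | 0.17 | 76 |
| 10% v 30% | 0.35 | 0.24 | 62 |
| 5% v 40% | 0.78 | 0.72 | 22 |
| 10% v 50% | 0.81 | 0.74 | 20 |

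Worked for the first row: p̄ = 0.125, so [1.96 × 0.468 + 0.8416 × 0.456]²/0.0225 = 1.690/0.0225 = 75.1, rounded up to 76.

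Only very large differences would be detected reliably, so the item should be used for estimation and not for a test.

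**The case against.** A reader might infer that the waiting-list group is asked nothing, that the randomised month cannot show harm at all, or that no between-group difference in any harm can be formed. The documents support none of these. Group 3 completes the ODI, the BPI, the medication and other-treatment questions and the perceived-need item. Section 5.1 compares ODI and BPI change with the waiting list, and the two-tailed level in section 5.2 covers worsening as well as benefit. For a back-pain treatment, more pain or disability is a central harm, and it has a concurrent control.

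It can also be said that this is a pilot without a safety hypothesis, that skin irritation from a belt is largely device-specific so a waiting-list rate would add little, that participants know their group, and that 20 per group cannot settle a modest difference. The limit of 16.8% for 0 of 20 comes from the group size and is the same with or without a new item.

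All of this stands and narrows the point. It does not cover symptoms that those scales miss or cannot identify. For these an imprecise comparison is more useful than none, and a pilot is a natural place to try the question.

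**Conclusion.** The point holds in a limited form. Attributed side effects are asked in groups 1 and 2 with different items and are not asked in group 3. Symptoms other than a change in pain or disability at the time of the visit therefore have no common question and no randomised comparator, in the only period that could supply one. Worsening of pain and disability does have a comparator; for that harm the data exist and what is missing is a planned count per group.

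The size of the loss cannot be stated as a rate, because the documents give no side-effect frequencies. The conclusion rests on the group labels in section 4.2.3 being read as in the table, and on the supplied text being complete for adverse events; it contains no separate adverse-event section. The ODI and BPI efficacy comparisons are unaffected. This is an inexpensive improvement worth making before the first month-1 visit.

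**What to change.** In section 4.2.3, under the all-participants label, add one neutral item, worded the same for the three groups and asked before the treatment-specific items. For example: *Since your last visit, have you had any new symptom, or has any symptom become worse? If so, what was it, when did it begin, and did you seek care for it?* Keep the existing exercise and belt items as additions.

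In section 5.2, state that for months 0 to 1 the following will be reported per group, descriptively and without a significance test:

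- the number and percent with any new or worsened symptom, with exact 95% intervals;
- the number and percent whose ODI worsened and whose BPI worsened from baseline, with the definition of worsening fixed in advance and carried-forward values shown separately.

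The second line uses data already collected. The cost is one questionnaire item for 60 participants and one table, with no extra visit, staff or procedure. The downside is that some unrelated complaints will be recorded, reports will be unblinded and intervals will be wide, so the table should be described as a comparison of reported symptoms and not as evidence of causation.
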